12.1. Sample Size Determination

In our randomized Phase II trial of TAC and SIR vs. TAC and MTX as GVHD prophylaxis after allogeneic transplantation we observed an acute GVHD incidence of 43% (95% CI 30-63%) with TAC/SIR⁴. Simon's minimax two-stage design with 10% one-sided type I error and 10% type II error rate is used for study design as follows. We will consider 43% incidence of grade II-IV

acute GVHD (aGVHD) not warranting further study. We will use 23% incidence rate as a promising result to pursue further study. With these study parameters, 15 evaluable patients will be investigated in the first stage. If 7 or more of 15 evaluable patients experience the grade II-IV acute GVHD, the treatment will be stopped. Otherwise, once 9 or more of 15 patients completed the +90 (+/-14) days follow up without experiencing the grade II-IV acute GVHD 23 additional evaluable patients (a total of 38 evaluable patients) will be enrolled. If the number of patients experiencing the grade II-IV aGVHD is 12 or less, ($\leq 31.6\%$ incidence rate at day 100), the null hypothesis will be rejected and the regimen will be considered promising. An evaluable patient for primary endpoint is defined as patients who receive at least one dose of PANO per protocol and who neither relapse nor die of any reasons without experiencing grade II-IV aGVHD until day 100. A non-evaluable patient will be replaced and we anticipate a total of 44 patients will be accrued in order to account for 10% of competing risks (relapse or death without GVHD) at day 100.

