Pan-HDACi in allogeneic BMT may have different effects and encourages investigations to study the function of individual HDAC members which are not elucidated to date. PANO tested in murine models accelerated GVHD compared to vorinostat which was unexpected but has not translated in humans in 2 ongoing clinical trials discussed herein. Pathological changes in mice showed increased liver damage without significant changes in colon or small intestine. Changes were associated with increased systemic Th1 cytokines, enhanced CXCR3 expression on donor CD4⁺ and CD8⁺ T cells, and T cell infiltration in the liver³⁴.

In parallel to the development of murine models, we have tested the safety of PANO administered to patients with acute GVHD within 72 hours of initiation of glucocorticoid therapy (methylprednisolone 0.8 mg/Kg/day IV or equivalent for at least 14 days) as first line therapy. As of November 2014, We have enrolled 20 subjects, median age 53 years (range, 34-76), male (n=13)/female (n=7), white(n=15)/hispanic(n=5); with diagnosis of CLL (n=2), MDS (n=2), Myeloma (n=1), Follicular NHL (n=1), CML(n=1), Myelofibrois (n=3), AML (n=6), MDS/CMML (n=3) or ALL(n=1). Conditioning regimens included Busulfan(BU)/fludarabine(FLU) AUC 5300 (n=10) or AUC 3500 (n=3), FLU/Melphalan (n=5) or Pentostatin/BU (n=2); and GVHD prophylaxis for MUD 8/8 (n=11) or MRD (n=5) HCT with TAC/MTX (n=7), TAC/rapamycin(n=7)(sirolimus-SIR), TAC/MMF(n=3) and for mismatched transplants with either TAC/SIR/ATG (n=2) or TAC/MTX/ATG (n=1). Median day of acute GVHD (n=19) onset was day + 37 post HCT (26 -100 days) with overall grade GVHD II (n=) or III (n=6); and median day of acute symptoms in overlap GVHD patients (n=5) was day + 528 (109-981). All Patients were treated with voriconazole (n=14) or micafungin (n=5) for fungal prophylaxis. For the first four patients Panobinostat was administered intravenously (IV) weekly x 4 at 2.5MG/M2 (n=3) or 5MG/M2 IV (n=1) with all 4 achieving either CR (n=3) or PR (n=1) GVHD responses by day +15 of Panobinostat. Due to manufacturer discontinuation of IV

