9.1. AE definition: An adverse event (AE) is the appearance or worsening of any undesirable sign, symptom, or medical condition occurring after starting PANO that is unexpected with HCT. Table 8 describes criteria for “expected” toxicities for HCT/GVHD-related symptoms that are commonly observed in transplant patients. Certain Grade 4 toxicities under particular categories in the NCI CTCAE are common in the HCT transplant setting, and patients with Grade III or IV GVHD are likely to experience additional serious symptoms. These listed toxicities are likely related either to the HCT or preparatory and treatment regimens, however, the investigator must use best medical judgment in making an assessment as whether or not the study drug (PANO) may have had a contributory role.

Table 8. Expected Transplant/GVHD-Related Toxicities in HSC Transplant Patients.

Category	Symptoms/Event	Category	Symptom/Event
Dermatological	Pruritus Rash/dermatitis associated with high-dose chemotherapy or GVHD	Renal/Genitourinary	Bladder spasms/cystitis Creatinine elevation/renal failure Dysuria frequency-urgency Urinary retention
Constitutional	Fever, Rigors, Chills Headache Tremors Weight lost and gain Confusion due to medications Peripheral edema	Reproductive	Persistent amenorrhea
Gastrointestinal	Gastritis GERD Colitis Dehydration Diarrhea Nausea/vomiting Dysphagia Stomatitis/pharyngitis Hematocheza/melena Abdominal pain or cramping	Metabolic/Laboratory	Acidosis/alkalosis Amylase/lipase elevation Hypo-/Hyperglycemia Hypo-/Hyperkalemia Hypo-/hypercalcemia Hypo-/Hypermagnesium, Hypophosphatemia Hypo-/Hypernatremia Hypertriglyceridemia/Hyperlipidemia/hypercholesterolemia Hyperuricemia Increased LDH

Category	Symptoms/Event	Category	Symptom/Event
Hepatic	LFT elevation Bilirubin elevation Hypoalbuminemia Hepatomegaly	BMTComplex/ Multicomponent Events	GVHD* Stem-cell infusion complications Venoocclusive Disease/ascites
Cardio-vascular	Edema Hypertension/Hypotension Sinus tachycardia Arrhythmia (Atrial fibrillation/flutter; Sinus ventricular tachycardia and others) Vascular access complication- deep vein thrombosis requiring anticoagulation Thomboembolic event	Hematologic	Cytopenias Catheter associated venous thrombosis
Infections*	Bacterial, fungal and/or viral infections Sepsis/confusion		

*Infection and GVHD: These toxicities will not be considered AEs but data will be captured on eCRFs. Other toxicities will NOT be captured as expected HCT complications.

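### Section 12.1 has no stopping provision in stage 2, so accrual can continue after a 13th grade II-IV acute GVHD event has ruled out a promising result

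*Combined protocol and SAP*

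**What the plan says.** Section 12.1 sets the design: "Simon's minimax two-stage design with 10% one-sided type I error and 10% type II error rate is used for study design". The unacceptable rate is 43% ("We will consider 43% incidence of grade II-IV") and the target is 23% ("We will use 23% incidence rate as a promising result to pursue further study").

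- **Stage 1:** "15 evaluable patients will be investigated in the first stage". The stop is: "If 7 or more of 15 evaluable patients experience the grade II-IV acute GVHD, the treatment will be stopped". The trial proceeds "once 9 or more of 15 patients completed the +90 (+/-14) days follow up without experiencing the grade II-IV acute GVHD".
- **Stage 2:** 23 more evaluable patients are enrolled, 38 in all. The regimen is promising if 12 or fewer have an event. No rule applies between patients 16 and 38.
- **Evaluability:** only patients who relapse or die by day 100 without grade II-IV GVHD are dropped and replaced. A patient with the event is therefore evaluable once it occurs.

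Section 12.2 monitors only grade 3 or higher toxicity that is unexpected with transplant. Table 8 (section 9.1) lists GVHD as expected, and its footnote, covering infection and GVHD, says: "These toxicities will not be considered AEs but data will be captured on eCRFs". The monthly review in section 11.1 lists accrual, adverse events and protocol deviations or violations; it does not list GVHD counts.

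**The concern.** The 13th event in stage 2 settles the trial. No later outcome can bring the count back to 12, and replacing non-evaluable patients cannot remove an event. As written, accrual runs on to 38 evaluable patients, and each new patient is scheduled for 26 weeks of PANO (section 5.7.1.3) without being able to change the conclusion.

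The outcome being counted is also the harm that matters most if the drug does not work. Section 1.4 reports that "PANO tested in murine models accelerated GVHD compared to vorinostat". The same sentence adds that this has not carried over to humans in two ongoing trials, so worsening is a possibility and not an expectation. A simple lack of benefit is enough for the point to matter.

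**Working it through.** **Inputs.** From 12.1: p0 = 0.43, p1 = 0.23, n1 = 15, stop at 7 or more events, n = 38, success at 12 or fewer. From 3.3: 2 patients a month. From 1.4: acute GVHD onset at a median of day 37 (range 26 to 100) in an earlier treatment study. This last input is used only as an assumption about timing.

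**1. Reproduce the design.** Let X1 ~ Bin(15, p) and X2 ~ Bin(23, p).

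- P(stop in stage 1) = P(X1 ≥ 7) = 0.485 at 43% and 0.037 at 23%.
- P(promising) = Σ over x = 0 to 6 of P(X1 = x) · P(X2 ≤ 12 − x) = 0.0958 at 43% (type I error) and 0.9038 at 23% (power).
- Expected evaluable N at 43% = 15 + (1 − 0.4847) × 23 = 26.9.

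A full minimax search returns this same design, so the plan's figures are right.

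**2. When failure is certain.** Seven stage-1 events leave at most 15 − 7 = 8 GVHD-free patients, below the 9 needed. Thirteen events exceed 12. Both outcomes already count as failures, so halting accrual there leaves type I error and power exactly as they were.

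**3. How often stage 2 runs past its verdict.** At 43%, P(pass stage 1, then fail) = 1 − 0.4847 − 0.0958 = 0.4196. An exact recursion, with each outcome known at once, gives the position of the 13th event in those trials. The reduction in expected N is the second column times the fourth.

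| True rate | P(fail in stage 2) | Mean position of 13th event | Patients before the 38th | Expected N as written | Expected N, stage-2 rule added |
|---|---|---|---|---|---|
| 23% | 0.059 | 35.0 | 3.0 | 37.1 | 37.0 |
| 43% | 0.420 | 31.7 | 6.3 | 26.9 | 24.2 |
| 50% | 0.288 | 29.9 | 8.1 | 22.0 | 19.7 |
| 60% | 0.095 | 27.4 | 10.6 | 17.2 | 16.2 |

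**4. Allow for delayed onset.** The simulation used random entry at 2 a month, stage 2 opening only after the go rule is met, and non-evaluable patients ignored. Onset was either fixed at day 37 or uniform over days 26 to 100. Among trials failing in stage 2 at 43%:

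- fixed day 37: a mean of 4.2 patients enrolled after the 13th event, with at least one in 78% of such trials;
- uniform: a mean of 3.0, with at least one in 64%.

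Averaged over all trials at 43%, that is about 0.42 × 3.0 = 1.3 to 0.42 × 4.2 = 1.8 patients.

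**5. Stage 1 for comparison.** On the same assumptions at 43%, a trial failing in stage 1 enrols a mean of only 0.5 to 1.0 patient after the 7th event.

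**6. What the stage-2 rule leaves for estimation.** Passing stage 1 means at most 6 events, so a 13th needs at least 7 more patients: 15 + 7 = 22 at the earliest. At 43%, the mean naive proportion with GVHD is 46.2% with the stage-2 rule and 46.1% as written.

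**The case against.** An uncurtailed Simon design is standard, and stage 1 is itself the futility look: it stops 48.5% of trials at 43% and about 70% at 50%. This stands. Curtailment is an improvement, not the repair of an error.

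A reader might infer that GVHD is read only once all 15 patients, and later all 38, are complete. For stage 1 the text does not say so. The stop does not require all 15 to have finished follow-up, and the go decision is triggered by a count. Stopping at the 7th event fits the wording; the timing is just not stated.

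A reader might also infer that GVHD goes unmonitored. It does not. It is assessed weekly at a single site and recorded on the eCRFs, the PRMC monitors safety and progress, and a patient whose GVHD needs high-dose corticosteroids stops PANO individually (section 6.3). None of this is a rule on further accrual.

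Stopping at an event biases the incidence estimate upward and thins the correlative sample. This has force for stage 1. With immediate outcomes at 43%, curtailing both stages raises the mean naive estimate from 46.1% to 48.0% and leaves fewer than 15 PANO patients in 39% of trials, against the 15 v 15 comparison in section 12.5. It has little force for stage 2, where the estimate hardly moves and 22 or more patients cover the planned 20 v 20 comparison.

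Finally, the onset times come from 19 acute GVHD cases in a treatment study, and no delay for biopsy or grading was added. The lagged figures are therefore indicative only.

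**Conclusion.** The gap is real and lies in stage 2: no provision stops accrual once a 13th event has made success impossible, and no other stated rule counts GVHD. At a true 43%, this situation arises in 42% of trials. The excess in those trials is 6.3 patients if outcomes were known at once, and about 3 to 4 under the assumed onset times and 2 patients a month. Under a 23% rate almost nothing is lost by curtailing (expected N 37.1 against 37.0).

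The documents do not support calling this a flaw in the type I error, power or sample size, all of which reproduce. Nor do they support saying that patients will certainly be enrolled after failure is fixed: under the assumed timing, 22% to 36% of stage-2 failures at 43% enrol none. In stage 1 the issue is unclear wording with a small effect. The change is worth making because it costs one sentence and spares a few patients a treatment course that cannot alter the result.

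**What to change.** Add to section 12.1 that stage-2 accrual stops once the 13th grade II-IV acute GVHD event occurs among the first 38 evaluable patients, and that patients already enrolled are followed as planned. Limiting the count to the first 38 matters because 44 patients are to be accrued. If more than 38 prove evaluable, an event in a later patient must not trigger the rule; state that evaluable patients are counted in order of enrolment.

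Also clarify that the stage-1 stop may take effect at the 7th event among the first 15 evaluable patients. If it does, the report should acknowledge the smaller stage-1 sample for the incidence and correlative estimates.

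The changes concern accrual only. Whether patients already receiving PANO continue is a clinical matter that this point does not address.

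The work needed is a running count of events already assessed weekly. Type I error (9.6%) and power (90.4%) are unchanged. The price is a few fewer patients for the incidence, secondary and correlative estimates in a trial that has already failed, with at least 22 PANO patients available whenever the stage-2 rule acts.

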2.1. Primary Objective

To prospectively determine the cumulative incidence of acute GVHD grades II-IV by day 100 when combining PANO with standard combination of TAC/SIR for GVHD prevention. It is anticipated that the combination will decrease of acute GVHD risk to 30% compared to our historical control of 50% with TAC/SIR alone.

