2.2. Secondary Objectives

- 2.2.1. Clinical objectives:
 - 2.2.1.1. Cumulative incidence of chronic GVHD
 - 2.2.1.2. Engraftment, relapse, non-relapse mortality, overall and relapse-free survival at one year.
- 2.2.2. Biological studies to test the pharmacodynamics of TAC/SIR/PANO combination for GVHD prevention:
 - 2.2.2.1. Immune Reconstitution determined by flow cytometry
 - 2.2.2.2. Histone acetylation of T cells and DC subsets by Western Blot and flow cytometry
 - 2.2.2.3. T reg immune-reconstitution, Foxp3+ expression and acetylation by flow cytometry
 - 2.2.2.4. Inflammatory cytokine and Biomarker expression profiling
 - 2.2.2.5. Stat-3 activation and acetylation
 - 2.2.2.6. Panobinostat pharmacokinetics

	Objective	Endpoint
Primary Clinical Objectives	Prospectively determine the cumulative incidence of acute GVHD grades 2-4 using TAC and SIR in addition to PANO for GVHD prevention. Study parameters: We will consider $\geq 43\%$ incidence of grade II-IV aGVHD not acceptable. We will use 23% incidence rate of GVHD as target.	GVHD severity stage and grading and distribution will be measured weekly from day of transplant to day 90 +/- 14 using standard scoring system. Stage of GVHD will be given for each site of involvement (e.g. skin, liver, and gut), as well as a composite score for overall acute GVHD grade. Pathologic confirmation of aGVHD will be dictated by usual clinical practice, and not

		mandated by this protocol. Treatment of GVHD will not be mandated.
Secondary Clinical Objectives	Cumulative incidence of chronic GVHD	GVHD with onset after 100 days post-HCT with presence of at least one diagnostic manifestation of chronic c-GVHD or distinct manifestation confirmed by biopsy or other relevant tests (eg PFT). Classified as: 1- Classic chronic GVHD - meets criteria for chronic GVHD and has no features consistent with aGVHD or 2- Overlap syndrome - features of acute and chronic GVHD exist together. C-GVHD will be measured prospectively in all patients on days 90+/-14 , 120 +/- 14, 150 +/- 14, 180+/- 14, 270+/- 30, and 365 +/- 30 as per standardized scoring system.
	Engraftment	Stable engraftment for WBC is defined as a sustained absolute neutrophil count > 500 over 3 days without cytokine support. Stable platelet engraftments is defined as count of > 20,000 over 7 days without transfusion support. Time to engraftment is defined as time from day 0 to day of sustained engraftment per above criteria for both platelets and WBC.

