- 3.3. **Sample Size and accrual rate.** It is estimated that 2 patients will be entered into the treatment study each month, therefore, we anticipate 24 months for completion of the study that will require **n=44** total patients for the treatment arm. We are planning to enroll **n=20** patients for “external control patients”. We anticipate 0.5 patients/month for “external control” subjects and accrual will happen concomitant to treatment arm patients. Therefore a total of **64** subjects will be accrued in total including treatment arm and external control.
- 3.4. **Patient Follow up.** Patients will be evaluated weekly from day of transplant until day 100 to measure acute GVHD using standard scoring system (defined in Appendix A). Stage of GVHD will be assessed for each site of involvement (e.g. skin, liver, and gut), as well as a composite score for overall acute GVHD grade determined. Pathologic confirmation of aGVHD will be dictated by usual clinical practice. Patient will be followed on days +90 +/-14, 120 +/- 14, 150 +/- 14, 180+/- 14, 270+/-30, and 360 +/- 30 for chronic-GVHD assessment and adverse events toxicity assessment. Taper of immunosuppression is suggested- not mandatory and treatment of GVHD is not mandated (section 6.2-6.3).
- 3.5. **Withdrawal.** from the study will take place under the following circumstances: those patients who sign consent for the study, but fail to initiate treatment due to:
- 3.5.1. denial of coverage from insurance provider
 - 3.5.2. disease progression prior to initiation of treatment
 - 3.5.3. death prior to initiation of treatment
 - 3.5.4. withdrawal of patient consent at any time after therapy

4. Patient Population: Inclusion and Exclusion criteria

- 4.1. **Inclusion Criteria:**
- 4.1.1. Male or female

- 4.1.2. Age \geq 18 years or older at time of enrollment
 - 4.1.3. Signed informed consent
 - 4.1.4. Hematologic disorder requiring allogeneic hematopoietic cell transplantation
 - 4.1.5. LVEF \geq 45% by MUGA scan or echocardiogram
 - 4.1.6. FEV1, FVC, and DLCO adjusted \geq 50% of predicted values on pulmonary function tests
 - 4.1.7. Transaminases (AST, ALT) $<$ 3 times upper limit of normal values
 - 4.1.8. Creatinine clearance calculated \geq 50mL/min
 - 4.1.9. Karnofsky Performance Status Score \geq 60%.
 - 4.1.10. HLA matched 8/8 (A, B, C, DRB1) related or unrelated donor
- 4.2. **Exclusion Criteria:**
- 4.2.1. Active infection not controlled with appropriate antimicrobial therapy

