6. GVHD

Acute GVHD manifests clinically as involvement of the skin, gastrointestinal tract, and liver, either as an isolated site of involvement or in combination. The traditional grading scheme for GVHD was developed by Glucksberg, *et al*, in 1974. This grading

scheme was updated in 1995 with the publication of new consensus guidelines.⁴⁴ A major addition was the incorporation of persistent nausea with pathologic evidence of acute GVHD as grade 1 gastrointestinal GVHD. This established grading scheme will be utilized for the grading of this endpoint in the trial. (see Appendix A)

- 6.1. Evaluation procedures: Incidence of acute GVHD will be characterized by weekly clinical evaluations from day of transplant to day 90±10 using the above described objective standard scoring system. Organ stage of GVHD will be given for each site of involvement (e.g. skin, liver, and gut), as well as a composite grade for overall acute GVHD (see Appendix A). Pathologic confirmation of aGVHD will be dictated by usual clinical practice and it is highly encouraged, but not mandated by this protocol. If patients develop diarrhea while receiving PANO see recommended management in section 7.2. If patients develop isolated upper GI symptoms, pathology confirmation of GVHD is needed to score as GVHD.
- 6.2. Taper of immunosuppression is suggested- not mandatory- on days 50±3 for TAC or 365±30 for SIR in the absence of GVHD.
- 6.3. Therapy for established acute GVHD: Upon recognition of acute GVHD, standard treatment may involve high dose (1-2mg/kg) corticosteroids. The primary therapy of acute GVHD is not mandated by this protocol. Interval progress will be assessed on a routine basis by the treating physician. Without anticipated resolution, additional immunosuppression may be added per the treating physicians' discretion. The agents used, time of initiation, duration of exposure, interval response, and any specific toxicities will be recorded.

If GVHD develops and requires treatment with high dose corticosteroids (1-2mg/kg) while on planned PANO dosing schedule PANO should be stopped as failed primary endpoint.

7. Safety assessment:

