12.4 Analysis Plan for Primary Endpoint

The cumulative incidence rate of grade II-IV acute GVHD at day 100 is the primary endpoint of the study and will be estimated along with one-sided 90%

confidence interval using the approach proposed by Gray⁵⁰. The log-log transformation will be used to compute the point-wise confidence intervals. The death and relapse will be considered as competing risks of acute GVHD.

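### The primary endpoint is read at day 100, but the end of weekly acute GVHD grading is stated three ways and the stage-1 gate can count patients as event-free from day 76

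*Combined protocol and SAP*

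**What the plan says.** **Endpoint.** The objective in section 2.1 is the "cumulative incidence of acute GVHD grades II-IV by day 100". Section 12.4 agrees: "The cumulative incidence rate of grade II-IV acute GVHD at day 100 is the primary endpoint of the study". Section 12.1 also ties evaluability to day 100 (no relapse or death before then without grade II-IV acute GVHD) and states the final threshold as a day-100 incidence.

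**Weekly grading of acute GVHD.** Three end points are given:
- Section 2.2, objective and endpoint table: GVHD "will be measured weekly from day of transplant to day 90 +/- 14", so the last grading may fall on days 76-104.
- Section 6.1: "weekly clinical evaluations from day of transplant to day 90±10", so days 80-100.
- Section 3.4: "Patients will be evaluated weekly from day of transplant until day 100".

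Appendix C has no weekly column. It marks GVHD organ assessments at +90 and +120, each ±14 days, among other visits.

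**Stage-1 gate.** Section 12.1 stops treatment at 7 or more events in 15 evaluable patients. Otherwise the 23 further patients are enrolled "once 9 or more of 15 patients completed the +90 (+/-14) days follow up without experiencing the grade II-IV acute GVHD".

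**The concern.** The decision rule compares a count of events with a day-100 null rate of 43%, so the count should be complete to day 100 whenever it drives a decision.

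At stage 1 it need not be. A patient seen event-free on day 76 counts towards the nine, yet may still develop grade II-IV GVHD, relapse or die before day 100. The gate has no slack: nine event-free out of 15 leaves at most six events, and seven is the stopping number. If one of exactly nine counted patients has a later event and the other six have all had one, the total reaches seven after stage 2 has opened. Section 12.1 does not say whether accrual then stops.

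At the final analysis, a site that follows the table in 2.2 or section 6.1 may end weekly grading before day 100, while a site member who follows 3.4 may not. At stake are a weaker futility stop and, if late events were also lost from the final count, a count biased low against the 43% null.

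**Working it through.** **Inputs from section 12.1.** Null 43%, target 23%, "minimax two-stage design with 10% one-sided type I error and 10% type II error rate". n1 = 15, continue with 6 or fewer events; n = 38, promising with 12 or fewer events. Section 3.3 plans 2 treatment patients per month.

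**Assumption.** Let f be the share of day-100 events with onset after the early assessment. The documents do not give f; 5% and 10% are used. Section 1.4 reports, for the earlier panobinostat treatment cohort, that "onset was day + 37 post HCT (26 -100 days" were the median and range. This shows that late onset occurs but gives no share.

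**1. Reproduce the design.** P(pass stage 1) = P(X1 ≤ 6), X1 ~ Bin(15, p). P(promising) = Σ over x = 0..6 of P(X1 = x) · P(X2 ≤ 12 − x), X2 ~ Bin(23, p).

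| p | Pass stage 1 | Promising |
|---|---|---|
| 0.43 | 0.515 | 0.0958 (type I error) |
| 0.23 | 0.963 | 0.904 (power) |

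A search confirms 38 as the smallest feasible total. The design is correctly calculated for complete day-100 counts.

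**2. Upper bound at stage 1.** Suppose all 15 patients are read before their late events. The gate then sees p(1 − f): 0.43 × 0.95 = 0.4085 or 0.43 × 0.90 = 0.387. The final count is still complete to day 100.

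| f | Rate seen at gate | Pass stage 1 | Overall type I error |
|---|---|---|---|
| 0 | 0.430 | 0.515 | 0.096 |
| 5% | 0.4085 | 0.583 | 0.098 |
| 10% | 0.387 | 0.650 | 0.099 |

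With no gate at all, type I error is P(Bin(38, 0.43) ≤ 12) = 0.103, so no stage-1 error of this kind can push it higher.

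**3. At the planned accrual.** Two patients per month is one entry about every 15 days. When the ninth event-free patient reaches day 76, most of the other eight are already past day 100. Simulation used a true rate of 43%, entry every 15 days, each patient counted from day 76, a share f of events placed in days 76-100, and later events known as they occur. On average about 1.7 of the counted patients were still short of day 100. The chance of continuing was about 52% for f = 5% and 53-54% for f = 10%, against 51.5% by design. Random arrival times gave much the same result.

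**4. If the final count were cut early too.** Applying p(1 − f) to all 38 patients gives a type I error of 0.149 (f = 5%) or 0.219 (f = 10%).

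**The case against.** The strongest reply is that the plan already secures day-100 data. Section 3.4 requires weekly evaluation to day 100, section 10.12.1 records the onset date of acute GVHD, and Appendix C has a GVHD organ assessment at +120 that is not limited to chronic disease. The ±14 and ±10 windows also run forward, to day 104 and day 100. A reader might infer from the 2.2 table and 6.1 that ascertainment simply stops at day 90. The documents do not support that; they contradict one another.

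Nor do they support a reading in which the false-positive rate is 14.9-21.9%. That needs the final count to be truncated in every patient with no later capture, whereas 2.1, 12.1 and 12.4 all place the final count at day 100.

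It can also be said that the stopping rule itself carries no day-90 cut and applies to evaluable patients, so the gate may only time the opening of stage 2. Even on that reading, stage 2 opens while some counted patients are not yet classifiable as evaluable, and the consequence of a later seventh event is left open. The recorded onset date and the +120 visit can repair the final count, but not a stage-1 decision already taken.

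Finally, the earlier cohort consisted of patients treated because they already had GVHD, so its onset range cannot size the problem. That is accepted, and the range is not used for this purpose here.

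**Conclusion.** The inconsistency is real and should be corrected: two of the three stated grading windows, and the stage-1 gate, do not match the day-100 endpoint they serve. The numerical effect is modest. With 5-10% of day-100 events assumed to fall in days 76-100, the chance of continuing under the 43% null rises by about 1-2 percentage points at 2 patients per month. The figures of 58-65% are an upper bound that requires all 15 patients to be read early. Overall type I error remains near the 10% limit, with a ceiling of 10.3%, as long as the final count runs to day 100. The conflict in wording is certain; the size depends on the assumed share of late events and on accrual close to plan.

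**What to change.** - In the section 2.2 table and section 6.1, replace the day-90 windows with weekly grading through day 100, as in 3.4, and align Appendix C.
- In section 12.1, count a stage-1 patient as event-free only once day-100 status is known. This also removes the open question of a seventh event arising after stage 2 has started.
- State that the recorded onset date and the day-120 visit will be used to capture any onset up to day 100 in patients whose last weekly visit was earlier.

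The cost is protocol wording, one to three additional routine assessments in some patients, and a stage-1 look up to about three weeks later (100 − 76 = 24 days). Sample size and decision boundaries are unchanged.

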12.3 Population for Primary and Secondary Endpoints

Patients who receive at least one dose of the study drug (PANO) per protocol will be eligible for primary and secondary endpoints.

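### If 43% and 23% are day-100 cumulative incidences, the evaluable-only rule in 12.1 has about 81-85% power at the plan's own 10% competing risk, not 90%, with type I error of about 3-5%

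*Combined protocol and SAP*

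**What the plan says.** Section 12.1 sets a Simon minimax two-stage design with 10% one-sided type I error and 10% type II error. An incidence of 43% does not warrant further study and 23% is promising. The trial stops at 7 or more grade II-IV cases among 15 evaluable patients. With 12 or fewer among 38, "the null hypothesis will be rejected and the regimen will be considered promising".

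An evaluable patient has had at least one dose and is one "who neither relapse nor die of any reasons without experiencing grade II-IV aGVHD until day 100". For the rest, "A non-evaluable patient will be replaced". Accrual is set at 44 "in order to account for 10% of competing risks (relapse or death without GVHD) at day 100".

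The other sections describe a different quantity:

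- Section 2.1 gives the objective: "To prospectively determine the cumulative incidence of acute GVHD grades II-IV by day 100".
- The objectives table under 2.2 places 43% and 23% beside that objective: "We will use 23% incidence rate of GVHD as target".
- Section 12.3 defines the population: "Patients who receive at least one dose of the study drug (PANO) per protocol will be eligible for primary and secondary endpoints".
- Section 12.4 states: "The cumulative incidence rate of grade II-IV acute GVHD at day 100 is the primary endpoint of the study". It treats death and relapse as competing risks.
- Section 1.1 reports the historical 43% (95% CI 30-63%) as a 100-day cumulative incidence. Section 12.1 cites the same figure and interval as the source of its null.

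**The concern.** A cumulative incidence with competing risks divides GVHD cases by all dosed patients. The rule in 12.1 divides them by dosed patients minus those who relapsed or died first. The second denominator is smaller, so the same regimen shows a higher proportion under 12.1 than under 12.4. A null and target taken from the first scale and applied unconverted to the second make the rule harder to pass than stated. The plan uses its 10% competing risk to raise accrual but not to restate the error rates.

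This trial screens for activity ahead of a randomized study, so what is at stake is a false negative: a regimen that truly meets the 23% target is discarded more often than the 10% the plan states.

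**Working it through.** **Inputs.** From 12.1: p0 = 0.43, p1 = 0.23; continue if at most 6 of 15; promising if at most 12 of 38; competing risk 10%. The calculation assumes independent patients and full replacement to exactly 38 evaluable.

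**Formula.** P(pass | p) = sum over x = 0 to 6 of Bin(x; 15, p) × P[Bin(23, p) ≤ 12 − x].

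**Step 1: the plan's own figures.** With 43% and 23% used directly as proportions among evaluable patients, P(pass | 0.43) = 0.0958 and P(pass | 0.23) = 0.9038. The design reproduces at 9.6% type I error and 90.4% power. An exhaustive search confirms that 38 is the smallest total that meets both error limits.

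**Step 2: convert a cumulative incidence F to the evaluable scale.** The text allows more than one reading of the 10%.

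- Share q of dosed patients: F/(1 − q). This gives 0.43/0.9 = 47.8% and 0.23/0.9 = 25.6%.
- Share r of GVHD-free patients: F/[F + (1 − F)(1 − r)]. This gives 0.43/(0.43 + 0.57 × 0.9) = 45.6% and 0.23/(0.23 + 0.77 × 0.9) = 24.9%.
- Competing hazard held fixed, constant hazards, set to give 10% of dosed patients at F = 43%. The total hazard to day 100 is −ln(1 − 0.53) = 0.755, of which the competing part is 0.755 × 0.10/0.53 = 0.142. With that part unchanged and F = 23%, the competing risk is 11.6%, and 0.23/(1 − 0.116) = 26.0%.

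**Step 3: same rule, converted rates.**

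| Reading of 10% | Type I error | Power |
|---|---|---|
| No conversion (as stated) | 9.6% | 90.4% |
| 10% of dosed patients | 3.0% | 82.6% |
| 10% of GVHD-free patients | 5.2% | 84.8% |
| Hazard fixed from 10% at the 43% rate | 3.0% | 80.9% |

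**Step 4: sensitivity to the competing risk, 5% to 15%.**

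| Reading | Type I error | Power |
|---|---|---|
| Share of dosed | 5.7% to 1.3% | 87.1% to 76.8% |
| Share of GVHD-free | 7.2% to 3.6% | 87.9% to 81.0% |

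**Step 5: what the cut-off means on the 12.4 scale at 10%.** The limit 12/38 = 31.6% corresponds to a cumulative incidence of 0.316 × 0.9 = 28.4% (dosed) or 0.316 × 0.9/(1 − 0.1 × 0.316) = 29.3% (GVHD-free). Power of 90% needs a true cumulative incidence of 20.8% or 21.3%, not 23%.

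**Step 6: the other reading of 43% and 23%.** If they are proportions among evaluable patients, step 1 stands. The matching cumulative incidences are then 0.9 × 43% = 38.7% and 0.9 × 23% = 20.7% (dosed), or 0.43 × 0.9/(1 − 0.1 × 0.43) = 40.4% and 0.23 × 0.9/(1 − 0.1 × 0.23) = 21.2% (GVHD-free).

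**The case against.** **Section 12.1 may already be on the evaluable scale.** It labels its final cut-off of 31.6%, which is 12/38 among evaluable patients, as an incidence rate at day 100, the same term it uses for 23%. On that reading the design is correct. This stands as a possible reading. It does not settle the matter, because the 43% in the same paragraph is the figure that 1.1 reports as a cumulative incidence, and the table under 2.2 ties both rates to the cumulative-incidence objective. The shared label shows only that 12.1 treats the two scales as interchangeable.

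**The historical estimator is not named.** Section 1.1 does not say how competing events were handled, so placing 43% on the 12.4 scale is an assumption. It bears on the null and hence on the type I error. The 23% target and the endpoint in 12.4 do not depend on it.

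**The loss is modest.** The shift of roughly 2 to 5 percentage points in the rates is small beside the 30-63% interval around the historical 43%. That is fair, and it is why a wording change is enough.

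**The rule could be changed instead.** Counting 38 dosed patients, with competing events as non-cases, would restore 9.6% and 90.4% with the same cut-offs. That is a legitimate alternative, but it changes the decision rule and counts an early relapse or death as freedom from GVHD. Stating the scale does not require it.

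**Two stronger readings are not supported.** A reader might infer that leaving patients out makes it easier to declare success. The opposite holds: removing non-cases raises the observed proportion, and type I error falls. A reader might also infer that 12.1 and 12.4 can give rival decisions, for example 13/38 failing in 12.1 while the 12.4 upper limit lies below 43%. Section 12.4 only estimates the incidence with an interval and states no null or threshold. The one decision rule is in 12.1.

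**Conclusion.** The point holds, conditionally. The objective, the endpoint and the source of the 43% indicate cumulative incidences, while 12.1 applies the rates unconverted to evaluable patients. On that reading the rule does not deliver 90% power for the stated endpoint. At 10% competing risk, power is about 81-85%, so a regimen at a true 23% is rejected about 15-19% of the time instead of 10%. Type I error is about 3-5%, within the stated 10%, and no ineffective regimen is favoured.

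This rests on 43% and 23% being cumulative incidences and on the historical estimate having kept competing events in its denominator. It is a mismatch of scale and not an arithmetic error: if the rates are proportions among evaluable patients, 9.6% and 90.4% stand. All figures also assume that 43% and 23% are retained. The summary of rationale in 1.4 and section 2.1 give 50% against 30% instead, and that conflict has to be reconciled separately.

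**What to change.** In 12.1, adopt one of two statements.

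1. The 43% and 23% are day-100 cumulative incidences. Then say how the 10% competing risk is defined, restate power as about 81-85% and type I error as about 3-5% at 10%, and give the 5-15% sensitivity range (power about 77-88%).
2. The 43% and 23% are proportions among evaluable patients. Then give the matching cumulative incidences at 10% competing risk, about 39-40% and 21%, so that the 12.4 estimate is read against the right benchmark.

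Keep the cut-offs, the replacement rule and the sample size. The cost is a few sentences and, under the first option, a less favourable stated power.
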